4.1.3 WEEK 40/ET (DAY 280)

The following procedures must be performed and recorded at the Week 40/ET visit:

- 1. Update concomitant medication information.
- 2. Perform a brief physical exam.
- 3. Update AE information and record any new AEs.
- 4. Obtain UPT (WOCBP only) and evaluate results.
- 5. Collect blood pressure and pulse rate after the subject has been sitting quietly for 5 minutes.
- 6. Perform cutaneous tolerability evaluation (face only).
- 7. Perform lesion counts (face only).
- 8. Record areas treated since last visit (face, upper back, upper chest/shoulders).
- 9. Collect returned study drug and diary, perform accountability, and review study drug compliance with subject.
- 10. Review subject diary for completion.

4.1.4 DISCONTINUATION/WITHDRAWAL PROCEDURES

A subject may voluntarily withdraw from study participation at any time. If the subject withdraws consent and discontinues from the study, the Investigator will attempt to determine the reason for discontinuation and record the reason in the subject's study records and in the study database. If a subject is withdrawn because of an AE, that AE should be indicated as the reason for withdrawal. In the event of early discontinuation, (i.e., prior to Week 40/Day 280 visit) and whenever possible, the subject should be asked to return to the study center to complete the Week 40/ET evaluations. Subjects who withdraw from the study will not be replaced.

If at any time during the study the Investigator determines that it is not in the best interest of the subject to continue, the subject will be discontinued from participation. The Investigator can discontinue a subject at any time if medically necessary. The Investigator may discontinue a subject's participation if the subject has failed to follow study procedures or to keep follow-up appointments. Appropriate documentation in the subject's study record and the study database regarding the reason for discontinuation must be completed.

All subjects who fail to return to the study center for the Week 40/ET visit will be contacted by telephone to determine the reason(s) why the subject failed to return for the necessary visit or elected to discontinue from the study. If a subject is unreachable by telephone after a minimum of two documented attempts (one attempt on two different days), a certified letter will be sent requesting that the subject contact the Investigator.

Reasons for an Investigator's withdrawal of a subject may include, but are not limited to, the following:

- Safety (e.g., severe adverse reactions, pregnancy);
- Lack of efficacy as determined by the Investigator;
- When the requirements of the protocol are not respected (e.g., significant issues with study visit compliance);
- When a concomitant medication or treatment likely to interfere with the results of the study is reported, or required, by the subject (the Investigator will decide, in consultation with Chiltern, whether the subject is to be withdrawn);
- When a subject is lost to follow-up. The Investigator will try twice to reach the subject by telephone and will send a certified follow-up letter before considering that the subject is lost-to-follow-up. These actions will be reported on the subject's study record and a copy of the follow-up letter maintained in the Investigator's file.

Refer to Section 6.7 for a discussion of criteria for discontinuation of individual subjects from the study.

All premature discontinuations and their causes must be carefully documented by the Investigator on the subject's study record and in the study database. In no case will a subject who has been assigned a study number and entered into the study be replaced by another.

All Week 40/ET evaluations should be performed at the time of premature discontinuation. All data gathered on the subject prior to termination will be made available to Chiltern.

Study completion or reason(s) for discontinuation as listed in the study record will be entered into the study database as follows:

- Completed
- Adverse Event
- Lack of Efficacy
- Withdrawal by Subject
- Physician Decision
- Protocol Violation
- Lost to Follow-Up
- Pregnancy
- Worsening of condition
- Other

Novan has the right to terminate or stop the study at any time. Should this be necessary, the Investigator will ensure that proper study discontinuation procedures are completed.

4.2 TOLERABILITY ASSESSMENTS

The evaluator will assess the subject's face at baseline and each study visit. The cutaneous tolerability scores from Week 12 of NI-AC301 or NI-AC302 will be the subject's baseline tolerability. The cutaneous tolerability assessment should be performed at least 30 minutes after study drug application. Cutaneous tolerability evaluations will include erythema, scaling, dryness, pruritus and burning/stinging. Pruritus and burning/stinging will be based on the subject's report for the previous 24 hours. Cutaneous tolerability endpoints will not be reported as an AE unless they reach severe and/or result in subject's discontinuation from the study. Subjects who develop intolerance to the product as defined by scores of 3 (severe) on two or more categories of tolerability (erythema, scaling, dryness, pruritus, burning/stinging) shall be discontinued from the study. Cutaneous tolerability assessments will be performed according to the following scales:

Erythema

Score Description

0-None No evidence of erythema present

1-Mild Slight pink coloration

2-Moderate Definite redness

3-Severe Marked erythema, bright red to dusky dark red in color

Scaling

ScoreDescription0-NoneNo scaling

1-Mild Fine scales present to limited areas of the face, barely perceptible

2-Moderate Fine scale generalized to all areas of the face

3-Severe Scaling and peeling of skin over all areas of the face

Dryness

ScoreDescription0-NoneNo dryness

1-Mild Slight but definite roughness

2-Moderate Moderate roughness 3-Severe Marked roughness

Pruritus

Score Description
0-None No itching

1-Mild Slight itching, not very bothersome

2-Moderate Moderate amount of itching, somewhat bothersome

3-Severe Severe amount of itching, definite discomfort and sleep may be disturbed

Burning/Stinging

Score Description

0-None No burning/stinging

1-Mild Slight warm, burning/stinging sensation; not very bothersome

2-Moderate Definite warm, burning/stinging sensation that is somewhat bothersome

3-Severe Hot, tingling/sensation that has caused definite discomfort and may have

disturbed sleep

4.3 SAFETY ASSESSMENTS

Adverse events will be collected beginning with the Baseline Visit for this study. Adverse events that began during NI-AC301 or NI-AC302 that are ongoing at the conclusion of either study will be reported as AEs at Baseline in this long-term safety study (NI-AC303) and followed. The physical exam, vital signs and pregnancy test results from the Week 12 visit of NI-AC301 or NI-AC302 will be used as the subject's Baseline assessments for this long term safety study and be collected during the study.

4.3.1 ADVERSE EVENTS

AEs will be collected starting after the subject has signed the informed consent and completed any study assessment until the end of the final study visit. The date of onset, date ended, severity,

relationship to study drug, therapy required, and action taken regarding study drug and study participation will be reported for each AE.

See Section 6 for additional information regarding the evaluation of adverse events.

4.3.2 PHYSICAL EXAM

A brief physical exam will be performed at Week 40/ET. If clinically significant changes in the physical examination from Baseline are noted at the Week 40/ET visit, these will be recorded as adverse events.

4.3.3 VITAL SIGNS

Blood pressure and pulse rate will be collected at Weeks 4, 12, 24, 36 and 40/ET. Any clinically significant changes in vital signs from Baseline will be recorded as adverse events whether or not drug related.

4.3.4 PREGNANCY TESTING

All WOCBP must have a UPT at Weeks 4, 12, 24, 36 and 40/ET and if the result is positive, the subject will not be allowed to continue in the study. Refer to Section 6.4 for further information.

4.4 EFFICACY ASSESSMENTS

The same evaluator should perform lesion counting at Weeks 4, 12, 24, 36, and 40/ET. This should be the same evaluator that performed the Week 12 assessments for the NI-AC301 or NI-AC302 study. In the event that this is not possible due to unforeseen circumstances, a different evaluator may evaluate the subject. However, the same evaluator should evaluate subjects at the Baseline and Week 40/ET evaluations. The subject's Week 12 lesion counts from NI-AC301 or NI-AC302 will be considered the Baseline value for this study.

4.4.1 LESION COUNTS

The facial area lesion counts will be taken from the forehead, right and left cheeks, chin and nose. The lesion count groups will be inflammatory and non-inflammatory. Facial inflammatory lesions (pustules, papules, nodules and cysts) will be counted and recorded. Non-inflammatory lesions (open and closed comedones) will be counted and recorded. The following are definitions of each lesion type:

Inflammatory lesions are defined as follows:

Papule –A small, superficial, circumscribed, palpable lesion elevated above the skin surface, less than 10 mm in diameter

Pustule -A superficial elevated lesion that contains yellow fluid (pus) within or beneath the epidermis

Nodule –A firm (indurated) lesion greater than 10 mm in diameter and that is thicker or deeper than the average papule

Cyst - Spherical swelling that contains fluid or semisolid material

Non-inflammatory lesions are defined as follows:

Open comedones (blackhead) –Plugged follicular units with brown/black central debris Closed comedones (whitehead) –Plugged follicular units with white central debris

4.5 SCREEN FAILURES

A screen failure subject will be a person from whom informed consent is obtained but who does not meet the study eligibility requirements. Subjects will not be allowed to rescreen.

4.6 PROTOCOL DEVIATIONS

This study will be conducted as described in this protocol, except for an emergency situation in which the protection, safety, and well-being of the subject requires immediate intervention, based on the judgment of the Investigator (or a responsible, appropriately trained professional designated by the Investigator). In the event of a significant deviation from the protocol due to an emergency, accident, or mistake, the Investigator or designee must contact Chiltern at the earliest possible time by telephone.

5. PROHIBITED THERAPIES AND MEDICATIONS

Concomitant medications are any prescription or over-the-counter (OTC) preparations. Use of concomitant medications will be recorded on the concomitant medications study record and study database beginning at the Baseline Visit until the final evaluation (Week 40/ET).

Subjects will be permitted to apply non-comedogenic moisturizer or sunscreen on an as-needed basis. Moisturizer must not contain antibacterials and the subject must not change moisturizer and/or sunscreen used during the course of the study. If used, moisturizers and sunscreen must be applied at least 30 minutes after study drug application.

Subjects must not have used anti-acne treatments including topical or systemic antibiotics or retinoids as described in Section 3.7.3 prior to Baseline. These medications are also prohibited during the trial. Short term courses of antibiotics (\leq 14 days) for non-acne related illnesses and inhaled or intranasal steroids are permitted during the trial.

Subjects may not be concurrently on drugs associated with exacerbating acne vulgaris (Appendix 16.1). Subjects must not participate in a different interventional research study during the study period.

Any medication/therapy used by the subject following first application of study product will be considered a concomitant medication/therapy (e.g., aspirin, acetaminophen, birth control pills, vitamins, etc.). Every attempt should be made to keep concomitant medication/therapy dosing constant during the study. Any change to concomitant medications/therapies should be noted on the subject's study record and in the study database. When applicable, an AE should be completed for any subject starting a concomitant medication/therapy after enrollment into the study.

6. EVALUATION OF ADVERSE EVENTS

6.1 DEFINITIONS

An adverse event (AE) is any untoward medical occurrence (e.g., sign, symptom, disease, syndrome, intercurrent illness, clinically significant abnormal laboratory finding, injury or accident) whether or not considered drug related. Any AE that emerges or worsens following administration of the informed consent and until the end of study participation will be collected. A pre-existing condition is one that is present prior to the start of the study and is to be reported as part of the subject's medical history unless it began as an AE in NI-AC301 or NI-AC302. Adverse events that began during NI-AC301 or NI-AC302 that are ongoing at the conclusion of either study will be reported as AEs at Baseline in this long-term safety study (NI-AC303) and followed. Prior conditions should be reported as an AE if the frequency, intensity, or the character of the condition worsens during the study or if the condition persists.

An adverse event or suspected adverse reaction is considered "unexpected" if it is not listed in the Investigator's Brochure or is not listed at the specificity or severity that has been observed.

A serious adverse event (SAE) includes any event, if in the view of either the investigator or the Medical Monitor results in any of the following outcomes:

- Death
- Life-threatening event (i.e., the subject was, in the opinion of the Investigator, at immediate risk of death from the event as it occurred. It does not apply to an AE that hypothetically might have caused death if it were more severe)
- Persistent or significant disability/incapacity (i.e., the AE results in a substantial disruption of the subject's ability to carry out normal life functions)
- Requires in-patient hospitalization or prolongs hospitalization (i.e., the AE required at least a 24-hour in-patient hospitalization or prolonged a hospitalization beyond the expected

length of stay; hospitalizations for elective medical/surgical procedures, scheduled treatments, or routine check-ups are not SAEs by this criterion)

- Congenital anomaly/birth defect (i.e., an adverse outcome in a child or fetus of a subject exposed to the molecule or investigational product before conception or during pregnancy)
- Does not meet any of the above serious criteria but may jeopardize the subject or may require medical or surgical intervention to prevent one of the outcomes listed above (i.e., is a significant or important medical event)

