7.5 SAFETY

7.5.1 ADVERSE EVENTS

All AEs that occur during the study or continue after enrollment into this study will be recorded and classified on the basis of MedDRA terminology. Treatment-emergent adverse events (TEAEs) are defined as AEs reported on or after the first day of enrollment in this long term safety study.

All information pertaining to an AE noted during the study will be listed by subject, detailing verbatim term given by the PI or designee, preferred term, system organ class (SOC), onset date, resolution date, severity, seriousness, action taken, outcome, and drug relatedness. The event onset will also be shown relative (in number of days) to date of first dose in this study.

Treatment-emergent AEs will be summarized by the number of subjects reporting a TEAE, SOC, preferred term, severity, relationship to study drug (causality), and seriousness. When summarizing AEs by severity and relationship, each subject will be counted only once within a system organ class or a preferred term by using the event with the highest severity and greatest relationship within each classification.

Adverse events will also be summarized by windows of exposure to study drug. The windows will include but are not limited to: 1) within the first 24 hours of exposure, 2) up to 1 month of exposure, 3) up to 3 months of exposure, 4) up to 6 months of exposure and 5) up to 12 months of exposure.

AEs will also be summarized based on extent of exposure as described in Section 7.7

Serious AEs will be summarized by severity, and relationship to study drug, and individual SAEs will be listed by subject. In addition, a list of subjects who prematurely discontinue from the study due to an AE will be provided.

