#### 4.5 Safety

#### 4.5.1 Adverse Events

All AEs that occur during the study or continue after enrollment into this study will be recorded and classified on the basis of Medical Dictionary for Regulatory Activities (MedDRA) terminology version 18.1. Adverse events ongoing at end of the pivotal study will be carried forward to this study, will not be considered treatment-emergent for this study, and will be summarized separately by SOC, PT, and relatedness. Treatment-emergent AEs (TEAEs) will be defined as AEs reported on or after the first day of enrollment in this long term safety study.

All information pertaining to an AE noted during the study will be listed by subject, detailing verbatim term given by the Investigator or designee, preferred term, system organ class (SOC), onset date, resolution date, severity, seriousness, action taken, outcome, and drug relatedness. The event onset will also be shown relative (in number of days) to date of first dose in this study.

Treatment-emergent AEs will be summarized by the number of subjects reporting a TEAE, SOC, preferred term, severity, relationship to study drug (causality), and seriousness. When summarizing AEs by severity and relationship, each subject will be counted only once, within a system organ class or a preferred term, by using the event with the highest severity and greatest relationship within each classification.

Serious AEs will be summarized by severity, and relationship to study drug, and individual SAEs will be listed by subject. In addition, a list of subjects who prematurely discontinue study drug due to an AE, had AEs leading to treatment modification, and AEs that resulted in death will be provided.

Adverse events will also be summarized by windows of duration of exposure to study drug to determine if there is a safety signal due to duration of exposure. The windows of exposure will include but are not limited to: 1) within the first 24 hours (i.e. Day 1 of the LTS study), 2) up to 1 month (i.e. 2-30 days), 3) up to 3 months (i.e. 31-90 days), 4) up to 6 months (i.e. 91-180 days) and 5) up to 12 months (i.e. 181-365 days).

Adverse event incidence will also be summarized by the extent of exposure categories (in grams) as described in section 4.4.

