Source: Listing xx.x.x.x, Program: xxxxx.sas, Output: T\_xx.x\_x\_xxxx.rtf, Generated on: DDMMMYYYY HH:MM

Protocol Number: NI-AC303

Using shell 14.3.2.1, Repeat table for the following:

Table 14.3.2.2 Shift from Baseline in Cutaneous Tolerability Evaluation - Scaling - Summarized Continuously by Study Visit Safety Population

Table 14.3.2.3 Shift from Baseline in Cutaneous Tolerability Evaluation - Dryness - Summarized Continuously by Study Visit Safety Population

Table 14.3.2.4 Shift from Baseline in Cutaneous Tolerability Evaluation - Pruritus - Summarized Continuously by Study Visit Safety Population

Table 14.3.2.5 Shift from Baseline in Cutaneous Tolerability Evaluation - Burning/Stinging - Summarized Continuously by Study Visit Safety Population

Protocol Number: NI-AC303

Table 14.3.3.1

Treatment Emergent Adverse Events (TEAE) Overview
Safety Population

Number of Subjects with	SB204 Experienced (N=XXX)	SB204 Naïve (N=XXX)	Overall (N=XXX)
Any TEAE	xx (xx.x)	xx (xx.x)	xx (xx.x)
Number of TEAEs	xx	xx	
Treatment-Related TEAE Number of Treatment-Related TEAEs	xx (xx.x)	xx (xx.x)	xx (xx.x)
	xx	xx	xx
TEAE Leading to Treatment Modification	xx (xx.x)	xx (xx.x)	xx (xx.x)
Number of TEAE Leading to Treatment Modification	xx	xx	xx
Treatment-Related TEAE Leading to Treatment Modification Number of TRTEAE Leading to Treatment Modification	xx (xx.x)	xx (xx.x)	xx (xx.x)
	xx	xx	xx
TEAE Leading to Treatment Discontinuation	xx (xx.x)	xx (xx.x)	xx (xx.x)
Number of TEAE Leading to Treatment Discontinuation	xx	xx	xx
Treatment-Related TEAE Leading to Treatment Discontinuation Number of TRTEAE Leading to Treatment Discontinuation	xx (xx.x)	xx (xx.x)	xx (xx.x)
	xx	xx	xx
Serious TEAE	xx (xx.x)	xx (xx.x)	xx (xx.x)
Number of Serious TEAEs	xx	xx	xx
Treatment-Related Serious TEAE	xx (xx.x)	xx (xx.x)	xx (xx.x)
Number of Treatment-Related Serious TEAEs	xx	xx	xx
TEAE Leading to Death	xx (xx.x)	xx (xx.x)	xx (xx.x)
Number of TEAE Leading to Death	xx	xx	xx
Treatment-Related TEAE Leading to Death	xx (xx.x)	xx (xx.x)	xx (xx.x)
Number of Treatment-Related TEAE Leading to Death	xx	xx	

Note: TEAE onset is based on the start of treatment in the LTS. Adverse events were coded using MedDRA 18.1. TR=Treatment-Related.

Source: Listing xx.x.x.x, Program: xxxxx.sas, Output: T\_xx.x\_x\_x\_x\_xxx.rtf, Generated on: DDMMMYYYY HH:MM

Protocol Number: NI-AC303

Table 14.3.3.2.1

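### Protocol 6.1 gives two opposite instructions for a stable pre-existing condition, and the plan's TEAE definitions disagree on whether such an entry would be counted

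*Protocol*

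**What the plan says.** **What is recorded as an AE (Protocol 6.1, one paragraph).**

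- The collection rule covers "Any AE that emerges or worsens following administration of the informed consent" and does not mention persistence.
- A condition present before the study "is to be reported as part of the subject's medical history unless it began as an AE in NI-AC301 or NI-AC302".
- AEs that began in a pivotal study and are still ongoing are reported as AEs at Baseline and followed.
- The closing sentence makes prior conditions reportable as AEs if the frequency, intensity or "the character of the condition worsens during the study or if the condition persists". It sets no limit on which prior conditions it covers.

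**What counts as a TEAE.**

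- Protocol 7.5.1: TEAEs "are defined as AEs reported on or after the first day of enrollment in this long term safety study".
- SAP 4.5.1: "Treatment-emergent AEs (TEAEs) will be defined as AEs reported on or after the first day of enrollment in this long term safety study".
- SAP 4.5.1, the only exclusion: "Adverse events ongoing at end of the pivotal study will be carried forward to this study, will not be considered treatment-emergent for this study". SAP 4.3 says the same.
- Notes to SAP Tables 14.3.3.1, 14.3.3.2.2 and 14.3.3.13 and Listing 16.2.8.1: "TEAE onset is based on the start of treatment in the LTS".
- Note to SAP Table 14.3.3.2.1: no such statement. It says only that duration of exposure runs from the first SB204 dose, which may fall in the previous study.
- Protocol synopsis, Statistical Methods: the summaries take AEs that occurred on or after the Baseline date.

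**The concern.** Take a subject with a chronic condition present at entry and unchanged at Week 4. One sentence of Protocol 6.1 puts it in medical history and another makes it an AE. The protocol itself expects such subjects, since section 5 permits inhaled and intranasal steroids during the trial.

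If a site follows the second sentence, the SAP's body text has no test that would remove the entry. The definition turns on reporting, with no condition on onset or worsening, and the one exclusion covers only AEs carried over from the pivotal studies. The table notes would remove it. Two programmers working from the same SAP could therefore produce different counts.

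AEs are a listed safety endpoint of a single-arm, open-label study planned for about 100 sites (Protocol 7.9). No concurrent control arm would show that part of the TEAE rate reflects how each site read one clause.

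**Working it through.** The plan states no figure on this point, so there is none to reproduce. The check is a comparison of texts followed by an illustration of size.

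**Step 1: one case under each rule.** The case is a medical-history condition with onset before the study, unchanged, and recorded as an AE at Week 4 under the persistence clause.

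| Source | Test applied | Counted as a TEAE? |
|---|---|---|
| Protocol 7.5.1 and SAP 4.5.1 body text | Reported on or after first enrollment day | Yes |
| SAP 4.5.1 exclusion | Ongoing AE from the pivotal study | Does not apply |
| Notes to Tables 14.3.3.1, 14.3.3.2.2, 14.3.3.13 and Listing 16.2.8.1 | Onset relative to start of LTS treatment | No, if the true onset date is entered |
| Protocol synopsis | Occurred on or after Baseline | No, if occurrence means onset |
| Table 14.3.3.2.1 note | No TEAE rule of its own | Falls back on the body text |

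The last row matters because the Table 14.3.3.2.1 shell is reused for the other duration-of-exposure tables (related, treatment modification, discontinuation, serious and fatal TEAEs). Its columns start at the first 24 hours of exposure, so it has no place for an event that began before exposure.

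**Step 2: size under the body-text rule.**

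- N = 600, the approximate enrollment in Protocol 7.9.
- h = share of subjects with an unchanged prior condition recorded as an AE. The documents give no value; 10–20% is assumed.
- p = share of subjects with a genuine new or worsened event. The documents give no value; 10–30% is assumed.
- h and p are assumed independent.

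Apparent incidence = 1 − (1 − p)(1 − h). Subtracting p gives the subjects added: N × h × (1 − p).

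| h | p = 10% | p = 20% | p = 30% |
|---|---|---|---|
| 10% | 600 × 0.10 × 0.90 = 54 | 600 × 0.10 × 0.80 = 48 | 600 × 0.10 × 0.70 = 42 |
| 20% | 600 × 0.20 × 0.90 = 108 | 600 × 0.20 × 0.80 = 96 | 600 × 0.20 × 0.70 = 84 |

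The range is 42 to 108 subjects. For h = 10% and p = 10%, for example, the any-TEAE count goes from 60 (10%) to 114 (19%).

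**Step 3: size under the onset rule.** Such entries do not count, so the number added is 0 for any h, provided the pre-study onset date is recorded correctly.

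**The case against.** The strongest reply is that the rest of the plan shows what was intended.

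- The persistence clause directly follows the sentence on AEs carried forward from NI-AC301/302 and may be meant only for those, which the SAP excludes from the TEAEs.
- The sample medical-history listing (16.2.4.2) shows an ongoing condition. The physical-exam listing (16.2.4.4) sends findings that predate the study to medical history. The vital-signs listing (16.2.7.4) ties AE reporting to post-baseline findings.
- Entrants must be in good general health, and the open AE question in Protocol 6.2 does not prompt for stable disease.
- Most of the TEAE notes already use onset.
- An unchanged condition would not ordinarily be judged related or serious, or a cause of discontinuation or death, so those displays should be little affected.

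Much of this stands. It confines the likely effect to the any-TEAE row and its SOC/PT rows, and it makes the onset rule the probable intention. It does not remove the conflict. The clause is written for prior conditions in general, and the sentence before it already requires ongoing pivotal AEs to be reported, so limited to those it would add nothing. Table notes that disagree with the SAP's own definition leave the question open.

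A reader might infer something stronger: that the SAP counts every AE by report date, so that the acne itself becomes a TEAE and the any-TEAE rate approaches 100%. The documents do not support this. Acne has no written exemption of the kind Protocol 4.2 gives to tolerability signs, but no passage tells sites to report stable acne as an AE. It is followed through lesion counts and has its own discontinuation reasons (lack of efficacy, worsening of condition), and the onset notes would exclude it.

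A reader might also multiply 600 by 10–20% and report 60–120 added subjects. That ignores those who would have a genuine TEAE anyway.

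**Conclusion.** The contradiction within Protocol 6.1 is plain on the page, as is the presence of three different TEAE anchors: report, onset relative to LTS treatment start, and occurrence from Baseline. Followed literally, the body text can count unchanged medical-history conditions as TEAEs, while the table notes would not.

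The size cannot be known from the documents. The 42 to 108 of 600 under the body-text rule depends entirely on the assumed shares and their independence. The zero under the onset rule depends on correct onset dates. Even then, the AE listings would still differ between sites that read the clause differently. The point should be corrected. It does not show that the TEAE tables will be inflated, only that the plan does not settle whether they can be.

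**What to change.** **Protocol 6.1.** Delete the persistence clause, or limit it to AEs carried forward from NI-AC301/302.

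**Protocol 7.5.1, SAP 4.5.1 and every TEAE shell, including Table 14.3.3.2.1.** Use one definition: *AEs with onset, or worsening of a pre-existing condition, on or after the first LTS dose*. Bring the synopsis wording into line. The worsening limb is needed because an onset-only rule could drop a prior condition that gets worse on SB204, which Protocol 6.1 makes reportable. SAP 4.3 and 4.5.1 exclude carried-forward AEs without exception, so the SAP should also say whether one that worsens during LTS treatment counts.

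A sentence on how the acne under study is handled in AE reporting would help sites.

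**Cost.** One protocol clause, a memo to sites, one SAP sentence with matching table notes, and possibly moving some entries already recorded as AEs to medical history. No new data are needed.
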